9. SAFETY EVALUATION

Summaries and analysis of safety data will be presented for the Safety Analysis Population.

Solicited AEs will be summarized by severity for each day post vaccination (Days 1-8) and as the maximum severity over all 8 days. Additionally, solicited AEs will be analyzed by taking the most severe response over the follow-up period, dichotomizing into a binary variable (none versus mild, moderate, or severe) and using standard techniques, such as exact confidence intervals (CI), to summarize the proportion of subjects reporting each symptom, any application site symptom, and any systemic symptom.

Unsolicited non-serious AEs will be collected from the time of first vaccination through 28 days after the last vaccination. Unsolicited AEs will be coded by MedDRA[®] for preferred term and system organ class (SOC). All SAEs, MAAEs and NOCMCs will be collected from the time of first vaccination through the end of the study (Day 394). The numbers of SAEs and MAAEs will be reported by detailed listings showing the event description, MedDRA[®] preferred term and SOC, relevant dates (vaccinations and AEs), severity, relatedness, and outcome for each event. Non-serious unsolicited AEs will be summarized as number and percentage of subjects reporting at least one event in each MedDRA[®] preferred term and SOC, cross-tabulated by severity and relationship to study product. Additionally, the proportion of subjects and exact 95% CIs of AEs in aggregate and by MedDRA[®] categories will be computed.

Clinical laboratory data will be summarized by severity and relationship for each visit, and as the maximum over all post-vaccination visits. Graphical presentations will include bar plots.

9.1. Demographic and Other Baseline Characteristics

Summaries of age, sex, ethnicity, and race will be presented by Treatment Group ([Table 15](#), [Table 16](#), [Table 17](#), [Table 18](#), [Table 19](#), and [Table 20](#)). Ethnicity is categorized as Hispanic or Latino, or not Hispanic and not Latino. In accordance with NIH reporting policy, subjects may self-designate as belonging to more than one race or may refuse to identify a race, the latter reflected in the CRF as “No” to each racial option.

Individual subject listings will be presented for all demographics ([Listing 6](#)).

9.1.1. Prior and Concurrent Medical Conditions

All current illnesses and past pre-existing medical conditions will be MedDRA[®] coded using MedDRA dictionary version 23.0r higher.

Summaries of subjects' pre-existing medical conditions will be presented by Treatment Group ([Table 21](#), [Table 22](#), and [Table 23](#)).

Individual subject listings will be presented for all medical conditions ([Listing 7](#)).

9.1.2. Prior and Concomitant Medications

Summaries of medications that were started prior to dosing and continuing at the time of dosing will be presented by WHO Drug Terms 2 and 3 and Treatment Group ([Table 314](#), [Table 315](#), and [Table 316](#)).

Individual subject listings will be presented for all concomitant medications ([Listing 17](#)).

9.2. Measurements of Treatment Compliance

The number of doses of study product administered to subjects will be presented by Treatment Group as part of the subject disposition table (Table 10, Table 11, and Table 12).

9.3. Adverse Events

When calculating the incidence of adverse events (i.e., on a per subject basis), each subject will only be counted once and any repetitions of adverse events within a subject will be ignored; the denominator will be the total population size. All adverse events reported will be included in the summaries and analyses.

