**Table 13: Treatment Arms and Substudy Dosing**

Cohort	Sample Size**	Stratum (Years of Age)	First and Second Dose in Main Study	Optional Third Dose in Substudy
1	15	18-55	25 mcg mRNA-1273	100 mcg mRNA-1273
2	15	18-55	100 mcg mRNA-1273	100 mcg mRNA-1273
3	15	18-55	250 mcg mRNA-1273	100 mcg mRNA-1273
4	10	56-70	25 mcg mRNA-1273	100 mcg mRNA-1273
5	10	56-70	100 mcg mRNA-1273	100 mcg mRNA-1273
6*	10	56-70	250 mcg mRNA-1273	n/a
7	10	≥71	25 mcg mRNA-1273	100 mcg mRNA-1273
8	10	≥71	100 mcg mRNA-1273	100 mcg mRNA-1273
9*	10	≥71	250 mcg mRNA-1273	n/a
10	15	18-55	50 mcg mRNA-1273	100 mcg mRNA-1273
11	10	56-70	50 mcg mRNA-1273	100 mcg mRNA-1273
12	10	≥71	50 mcg mRNA-1273	100 mcg mRNA-1273
13*	15	18-55	10 mcg mRNA-1273	n/a

\*Cohorts 6, 9 and 13 were not enrolled.

\*\*\*Four subjects did not receive the second dose of mRNA-1273 in the main study. Three subjects discontinued due to an AE (hives on lower extremities judged related to the first mRNA-1273 vaccination [cohort 1], sore throat [cohort 3], and maculopapular rash [cohort 5]); the other subject discontinued treatment due to quarantine for a COVID-19 exposure (cohort 1).

The third mRNA-1273 vaccination will be offered to subjects who received 2 doses of 25 or 50 mcg (cohorts 1, 4, 7, 10, 11, and 12), which are lower than the EUA mRNA-1273 dosage of 100

mcg, as soon as feasible after their Main Study Day 209 visit, and also will be offered to subjects who received 2 doses of 100 and 250 mcg (cohorts 2, 3, 5, and 8) no later than the close of the window for their originally scheduled Main Study Day 394 visit.

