9.3.1. Solicited Events and Symptoms

Systemic solicited adverse events were collected pre-vaccination, and systemic and local solicited adverse events were collected 30 minutes post-vaccination and then daily for 7 days after each vaccination and graded on a scale of 0 (absent), 1 (mild), 2 (moderate) and 3 (severe). Systemic events include: fatigue, headache, myalgia, arthralgia, nausea, chills and fever. Local events include: pain at injection site, erythema, and induration.

The proportion of subjects reporting at least one solicited adverse event will be summarized for each solicited adverse event, any systemic symptom, any local symptom, and any symptoms. The 95% CI calculated using Clopper-Pearson methodology from a binomial distribution (SAS Proc Freq with a binomial option) will be presented (Table 144, Table 145, and Table 146).

For each systemic and local event, any systemic event, any local event, and any solicited event, the maximum severity over 7 days after each vaccination will be summarized for the Safety population. The number and percentage of subjects reporting each event will be summarized by the maximum severity and treatment group, separately for each vaccination and over all vaccinations (Table 147, Table 148, Table 149, Table 150, Table 151, and Table 152). For each event the denominator is the number of subjects with non-missing data for the specific event.

The number of subjects reporting a solicited adverse event will be summarized for each day post vaccination for each vaccination and for all vaccinations combined both in a summary table starting at Table 153 and ending at Table 212 and graphically in a bar chart (Figure 122, Figure 123, Figure 124, Figure 125, Figure 126, and Figure 127).

The mean, standard deviation, median, minimum and maximum duration of solicited events will be summarized (Table 213, Table 214, Table 215).

Day of solicited symptom onset will be summarized graphically (starting at Figure 128 and ending at Figure 139).

Solicited adverse events by subject will be presented in listings (Listing 10 and Listing 11) and graphically (starting at Figure 140 and ending at Figure 175).

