9.3.2. Unsolicited Adverse Events

The proportion of subjects reporting at least one unsolicited adverse event will be summarized by MedDRA system organ class and preferred term for each vaccination and over all vaccinations.

Denominators for percentages are the number of subjects who received the vaccination being summarized.

Adverse events by subject will be presented in [Listing 12](#).

The following summaries for unsolicited adverse events will be presented by MedDRA system organ class, preferred term, vaccination and Treatment Group:

- Subject incidence and total frequency of adverse events (starting at [Table 216](#) and ending at [Table 228](#));
- Summary of severity and relationship to study product (starting at [Table 229](#) and ending at [Table 241](#));
- Subject incidence and total frequency of adverse events over time (starting at [Table 242](#) and ending at [Table 254](#));
- Subject listing of non-serious adverse events of moderate or greater severity ([Table 256](#));
- Listing of MAAEs and NOCMCs ([Table 257](#));
- Bar chart of non-serious adverse events by severity and MedDRA system organ class ([Figure 176](#), [Figure 177](#), and [Figure 178](#));
- Bar chart of non-serious adverse events by severity ([Figure 179](#), [Figure 180](#), and [Figure 181](#)).

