- c) For women of childbearing potential serum pregnancy test at screening, and urine or serum pregnancy test on Days 1 and 29 with results confirmed as negative prior to enrollment on Day 1 and administration of each vaccination.
- d) Depending on the timepoint approximately 8 or 16 mL of each venous blood sample is designated for secondary research.
- e) For those subjects consented for leukapheresis, screening procedures, including screening laboratory evaluations, will be performed locally prior to the leukapheresis procedure. Refer to the protocol-specific MOP for details on the leukapheresis procedure.
- f) Visits 09-14 windows should be based off the actual Visit 06 date.

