14.3.1.1 Solicited Adverse Events

Table 144: Number and Percentage of Subjects Experiencing Solicited Events by Symptom, Maximum Severity, Dose, and Treatment Group - Any Symptom - 18-55 Years of Age*

Symptom	Dose	Severity	25 µg mRNA-1273 (N=X)		50 µg mRNA -1273 (N=X)		100 µg mRNA -1273 (N=X)		250 µg mRNA -1273 (N=X)		All Subjects (N=X)	
			n	%	n	%	n	%	n	%	n	%
Any Symptom	Dose 1	None										
		Mild										
		Moderate										
		Severe										
	Dose 2	None										
		Mild										
		Moderate										
		Severe										
	Any Dose	None										
		Mild										
		Moderate										
		Severe										

Severity is the maximum severity reported over all solicited symptoms post dosing for each subject.
N=All subjects receiving Dose 1 with any solicited event data recorded in the database.

Tables with Similar Format:

Table 145: Number and Percentage of Subjects Experiencing Solicited Events by Symptom, Maximum Severity, Dose, and Treatment Group - Any Symptom – 56-70 Years of Age*

Table 146: Number and Percentage of Subjects Experiencing Solicited Events by Symptom, Maximum Severity, Dose, and Treatment Group - Any Symptom - ≥71 Years of Age*

Table 147: Number and Percentage of Subjects Experiencing Solicited Events by Symptom, Maximum Severity, Dose, and Treatment Group - Systemic Symptoms - 18-55 Years of Age*

			25 µg mRNA-1273 (N=X)		50 µg mRNA -1273 (N=X)		100 µg mRNA -1273 (N=X)		250 µg mRNA -1273 (N=X)		All Subjects (N=X)	
Symptom	Dose	Severity	n	%	n	%	n	%	n	%	n	%
Any Systemic Symptom	Dose 1	None										
		Mild										
		Moderate										
		Severe										
	Dose 2	None										
		Mild										
		Moderate										
		Severe										
	Any Dose	None										
		Mild										
		Moderate										
		Severe										
Arthralgia	Dose 1	None										
		Mild										
		Moderate										
		Severe										
	Dose 2	None										
		Mild										
		Moderate										
		Severe										

			25 µg mRNA-1273 (N=X)		50 µg mRNA -1273 (N=X)		100 µg mRNA -1273 (N=X)		250 µg mRNA -1273 (N=X)		All Subjects (N=X)	
Symptom	Dose	Severity	n	%	n	%	n	%	n	%	n	%
	Any Dose	None										
		Mild										
		Moderate										
		Severe										
Fatigue	Dose 1	None										
		Mild										
		Moderate										
		Severe										
	Dose 2	None										
		Mild										
		Moderate										
		Severe										
	Any Dose	None										
		Mild										
		Moderate										
		Severe										
Fever ^a	Dose 1	None										
		Mild										

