14.3.5 Displays of Laboratory Results

14.3.5.1 Chemistry Results

Table 259: Laboratory Results by Parameter, Maximum Severity, Time Point, and Treatment Group – Any Chemistry Parameter*

				None		Mild/ Grade 1		Moderate/ Grade 2		Severe/ Grade 3	
Timepoint	Treatment Group	N	N*	n	%	n	%	n	%	n	%
Screening (Day -42 to -1)	25 µg (18-55 years)										
	50 µg (18-55 years)										
	100 µg (18-55 years)										
	250 µg (18-55 years)										
	25 µg (56-70 years)										
	50 µg (56-70 years)										
	100 µg (56-70 years)										
	25 µg (≥71 years)										
	50 µg (≥71 years)										
	100 µg (≥71 years)										
	All Subjects										
Day 1, Baseline	25 µg (18-55 years)										
	50 µg (18-55 years)										
	100 µg (18-55 years)										
	250 µg (18-55 years)										
	25 µg (56-70 years)										
	50 µg (56-70 years)										
	100 µg (56-70 years)										
	25 µg (≥71 years)										

Timepoint	Treatment Group	N	N*	None		Mild/ Grade 1		Moderate/ Grade 2		Severe/ Grade 3	
				n	%	n	%	n	%	n	%
	50 µg (≥71 years)										
	100 µg (≥71 years)										
	All Subjects										
Day 8 (Days 7 to 9)	25 µg (18-55 years)										
	50 µg (18-55 years)										
	100 µg (18-55 years)										
	250 µg (18-55 years)										
	25 µg (56-70 years)										
	50 µg (56-70 years)										
	100 µg (56-70 years)										
	25 µg (≥71 years)										
	50 µg (≥71 years)										
	100 µg (≥71 years)										
All Subjects											
Day 29 (Days 27 to 31)	25 µg (18-55 years)										
	50 µg (18-55 years)										
	100 µg (18-55 years)										
	250 µg (18-55 years)										
	25 µg (56-70 years)										
	50 µg (56-70 years)										
	100 µg (56-70 years)										
	25 µg (≥71 years)										
	50 µg (≥71 years)										

				None		Mild/ Grade 1		Moderate/ Grade 2		Severe/ Grade 3	
Timepoint	Treatment Group	N	N*	n	%	n	%	n	%	n	%
	100 µg (≥71 years)										
	All Subjects										
Day 36 (Days 35 to 37)	25 µg (18-55 years)										
	50 µg (18-55 years)										
	100 µg (18-55 years)										
	250 µg (18-55 years)										
	25 µg (56-70 years)										
	50 µg (56-70 years)										
	100 µg (56-70 years)										
	25 µg (≥71 years)										
	50 µg (≥71 years)										
	100 µg (≥71 years)										
	All Subjects										
Max Severity Post Baseline	25 µg (18-55 years)										
	50 µg (18-55 years)										
	100 µg (18-55 years)										
	250 µg (18-55 years)										
	25 µg (56-70 years)										
	50 µg (56-70 years)										

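### The SAP gives conflicting denominators for adverse-event rates, and Tables 144–146 leave the Dose 2 denominator open

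*SAP*

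**What the plan says.** The primary endpoint counts solicited and unsolicited events after each vaccination (Protocol section 3; SAP 3.1). The SAP sets the denominator in five places:

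- **9.3**, for per-subject incidence of adverse events: "the denominator will be the total population size".
- **Shell footnote** under Tables 144, 147 and 150, which the other tables in 144–152 follow in format: "N=All subjects receiving Dose 1 with any solicited event data recorded in the database". Each shell has Dose 1, Dose 2 and Any Dose rows under one column N.
- **6.1**: percentages rest on the non-missing sample size. The N that annotates a table is the relevant population, missing observations included.
- **9.3.1**, for the maximum-severity summaries made "separately for each vaccination and over all vaccinations" and cited to Tables 147–152: "For each event the denominator is the number of subjects with non-missing data for the specific event".
- **9.3.2**, for unsolicited events: "Denominators for percentages are the number of subjects who received the vaccination being summarized".

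The 9.3.1 paragraph that assigns Clopper-Pearson intervals to Tables 144–146 states no denominator. The footnote to Protocol Table 13 records that "Four subjects did not receive the second dose of mRNA-1273 in the main study": two subjects in cohort 1, one in cohort 3 and one in cohort 5.

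**The concern.** For a Dose 2 row, 9.3 and the shell footnote lead to one denominator, and 6.1, 9.3.1 and 9.3.2 lead to another. The two differ wherever someone missed Dose 2. The SAP does not say which rule governs.

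The shells do not settle the question. Tables 144–152 list only the severities none, mild, moderate and severe. If N is Dose 1 recipients, a subject never given Dose 2 is either counted as having no reaction or left out, in which case the Dose 2 percentages sum to less than 100. The 9.3.1 rule asks for non-missing data on the event but does not name the dose.

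At stake are the post-Dose 2 reactogenicity rates, which are part of the primary endpoint. Protocol 12.2 reports that reactogenicity was generally greater after the second dose. The affected cohorts also fall at different dosages. At ages 18–55, the 25 and 250 mcg columns could shrink while the 50 and 100 mcg columns would not.

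A separate gap concerns unsolicited events. Section 9.3.2 asks for summaries by vaccination, but shells 216–254 have no such split, so its denominator rule cannot be applied in them.

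**Working it through.** **The plan's own figures.** The SAP states no Dose 2 N or rate. Its nearest figure is the probability of seeing at least one event at a 20% true rate, 1 − 0.8^n (SAP Table 3). For n = 15 this gives 96.5% and for n = 10 it gives 89.3%, both as stated. With the numbers who actually received Dose 2, it is 94.5% (n = 13), 95.6% (n = 14) and 86.6% (n = 9).

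**Inputs.** Planned cohort sizes are 15 (cohorts 1, 2, 3, 10) and 10 (cohorts 4, 5, 7, 8, 11, 12). They sum to 4 × 15 + 6 × 10 = 120, the number enrolled (Protocol 12.2). I take each planned size as the cohort's Dose 1 N. Subtracting the four subjects gives 13, 14 and 9 Dose 2 recipients in cohorts 1, 3 and 5.

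**Dilution factor** = Dose 2 recipients ÷ Dose 1 recipients:

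| Column | Dose 1 N | Dose 2 N | Factor | Largest understatement |
|---|---|---|---|---|
| Cohort 1 (25 mcg, 18–55) | 15 | 13 | 0.867 | 13.3 points |
| Cohort 3 (250 mcg, 18–55) | 15 | 14 | 0.933 | 6.7 points |
| Cohort 5 (100 mcg, 56–70) | 10 | 9 | 0.900 | 10.0 points |
| All 18–55 | 60 | 57 | 0.950 | 5.0 points |
| All 56–70 | 30 | 29 | 0.967 | 3.3 points |
| All ≥71 | 30 | 30 | 1.000 | 0 |

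The other seven enrolled cohorts have a factor of 1.

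**Rates with exact (Clopper-Pearson) 95% intervals:**

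| Cohort | Reactors | Over Dose 2 recipients | Over Dose 1 N |
|---|---|---|---|
| 1 | all 13 | 100% (75.3–100) | 86.7% (59.5–98.3) |
| 1 | 6 | 46.2% (19.2–74.9) | 40.0% (16.3–67.7) |
| 3 | all 14 | 100% (76.8–100) | 93.3% (68.1–99.8) |
| 3 | 7 | 50.0% (23.0–77.0) | 46.7% (21.3–73.4) |
| 5 | all 9 | 100% (66.4–100) | 90.0% (55.5–99.7) |
| 5 | 4 | 44.4% (13.7–78.8) | 40.0% (12.2–73.8) |

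**Unsolicited shells.** Tables 216–241 show counts only, so they have no percentage to dilute. Tables 242–254 show n and %, with no dose split.

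**The case against.** The strongest reply is that the specific rules govern. The 9.3 sentence is a general lead-in, and the two subsections after it set denominators by type of event. A subject never given Dose 2 has no Dose 2 data, so 6.1, 9.3.1 and 9.3.2 all exclude that subject. Section 6.1 makes the column N an annotation, and the fever footnote to Table 147 shows that a percentage denominator can differ from it. The 9.3.1 maximum-severity paragraph also names any solicited event, and the only shells with that content are Tables 144–146.

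Most of this stands. A reader might infer that the SAP does divide Dose 2 counts by Dose 1 recipients, so that the reported rates are diluted. The documents do not support that, because the footnote defines N and does not say that the Dose 2 percentage uses it.

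The reply does not remove the conflict. The non-missing rule is cited to Tables 147–152 and not to 144–146. The fever footnote cuts both ways, since an exception stated for fever alone may suggest that the other symptoms use the N defined beside it.

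A reader might also infer that the Day 36 laboratory row has the same flaw. It is labelled Days 35–37, yet "Visits 09-14 windows should be based off the actual Visit 06 date". With Visit 06 on Days 27–31 and Visit 09 six to eight days later, 6 of 15 permitted date combinations fall outside the label. That count is unweighted, and the SAP does not say that results outside the label are dropped. The note to Table 259 counts subjects who completed the visit. This is a labelling point, not a denominator flaw.

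**Conclusion.** The SAP is internally inconsistent on denominators for the primary safety endpoint. The part left open is the Dose 2 rows of Tables 144–146 and the exact intervals assigned to them. If the total population or Dose 1 N were used there, Dose 2 rates would be understated by up to 13.3, 6.7 and 10.0 percentage points in cohorts 1, 3 and 5. With about half of recipients reacting, the gap is 3 to 6 points. Four of 120 subjects and three of ten enrolled cohorts are involved. The trial tests no hypothesis (Protocol 9.1), so any effect on dose comparisons is on side-by-side estimates only.

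These sizes assume that Dose 1 numbers equal the planned cohort sizes, that the four listed subjects are the only ones without Dose 2, and that solicited data are otherwise complete. The missing vaccination split in shells 216–254 is a separate omission. It bears on percentages only in Tables 242–254.

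**What to change.** 1. Limit the 9.3 total-population sentence to any-dose or overall incidence. Keep it, because it is a proper rule there (Table 138, for example, uses the Safety Population).
2. State in 9.3.1 that Dose 2 rows, including those in Tables 144–146 and their intervals, use Dose 2 recipients with non-missing Dose 2 data.
3. Show a separate N for Dose 1, Dose 2 and Any Dose in Tables 144–152, and reword the footnote to match.
4. Add the split by vaccination to shells 216–254, with dose-recipient denominators in Tables 242–254.
5. Optionally, label the Day 36 laboratory row by days since the actual Dose 2 date.

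The cost is SAP wording and shell edits. No new data are needed.

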9.3.1. Solicited Events and Symptoms

Systemic solicited adverse events were collected pre-vaccination, and systemic and local solicited adverse events were collected 30 minutes post-vaccination and then daily for 7 days after each vaccination and graded on a scale of 0 (absent), 1 (mild), 2 (moderate) and 3 (severe). Systemic events include: fatigue, headache, myalgia, arthralgia, nausea, chills and fever. Local events include: pain at injection site, erythema, and induration.

The proportion of subjects reporting at least one solicited adverse event will be summarized for each solicited adverse event, any systemic symptom, any local symptom, and any symptoms. The 95% CI calculated using Clopper-Pearson methodology from a binomial distribution (SAS Proc Freq with a binomial option) will be presented (Table 144, Table 145, and Table 146).

For each systemic and local event, any systemic event, any local event, and any solicited event, the maximum severity over 7 days after each vaccination will be summarized for the Safety population. The number and percentage of subjects reporting each event will be summarized by the maximum severity and treatment group, separately for each vaccination and over all vaccinations (Table 147, Table 148, Table 149, Table 150, Table 151, and Table 152). For each event the denominator is the number of subjects with non-missing data for the specific event.

The number of subjects reporting a solicited adverse event will be summarized for each day post vaccination for each vaccination and for all vaccinations combined both in a summary table starting at Table 153 and ending at Table 212 and graphically in a bar chart (Figure 122, Figure 123, Figure 124, Figure 125, Figure 126, and Figure 127).

The mean, standard deviation, median, minimum and maximum duration of solicited events will be summarized (Table 213, Table 214, Table 215).

Day of solicited symptom onset will be summarized graphically (starting at Figure 128 and ending at Figure 139).

Solicited adverse events by subject will be presented in listings (Listing 10 and Listing 11) and graphically (starting at Figure 140 and ending at Figure 175).

